# Design:

# **Laboratory Practice Survey**

This part of the study will be conducted in England through the national network of Regional Cervical Screening Quality Assurance Directors, and in Wales and Scotland through Cervical Screening Wales and the Scottish Cervical Screening Programme respectively. A total of 39 laboratories from the 9 English QA regions, 7 from Scotland and 10 from Wales to be recruited to ensure an approximately even representation of the two current LBC systems, giving a total of 56 laboratories (28 laboratories for each system). They will include a cross-section of low, intermediate and high workload laboratories and all will have implemented LBC for population based cervical screening for a minimum of 6 months post LBC training and accreditation. This will avoid recognised learning curve issues. The suggestion that the NHS LBC pilot sites and training centres should supply the bulk of the cases is impractical given the substantial imbalance in representation of the two LBC companies across those sites and would be likely to greatly extend study timescales.

All participating laboratories will be asked to nominate a Study Liaison Officer and a deputy. These persons will normally be senior BMS staff and will act as the contact point for all communication with the LBC Adequacy Study Centre. Each laboratory will initially be asked to complete a questionnaire which will cover the following points:

- Type of LBC system used
- Approximate date of completion of LBC training
- Date of full conversion to LBC
- Criteria used in laboratory for assessing adequacy including declared threshold, with copy of relevant laboratory Standard Operating Procedure (SOP)
- Copy of any other relevant SOPs e.g. cell counting methodology
- Current KC61 figures (DH return giving laboratory performance data) or equivalent data but to include only LBC cases (some labs may not have full 12 months LBC data)

Additional laboratories may be recruited to increase the total number undertaking slide assessments and to spread this workload more widely. The same requirements for study entry will apply as stated above, but these laboratories will not be asked to complete a questionnaire or to submit slides. It will be important to ensure an approximately even representation of the two LBC

[figure not shown]

Figure 1- Examples of normal and additional slide labels

systems in all aspects of the study and on occasion this may require minor modifications to laboratory selection.

# **Slide Survey**

The 56 participating laboratories will be asked to submit 20 consecutive cervical screening LBC cases from each of the following report categories: inadequate, mildly dyskaryotic and high grade (moderate dyskaryosis and above). All high grade cases must be histologically confirmed. While histological confirmation of the mildly dyskaryotic cases is preferable it is acknowledged that this may not always be possible. It is important that as many cases as possible and certainly all high grade abnormalities are histologically proven to validate outcome. If outcome were determined by expert panel this could easily lead to a change in the original proffered diagnosis. This has serious and potentially negative implications for submitting laboratories and could lead to some declining participation.

Slides reported as borderline nuclear change will not be included in the study as this is a much less robust diagnostic category than higher grade abnormalities and its use is not consistently applied across laboratories.

50 consecutive negative cervical cytology LBC cases from the same time period will also be requested from each of these laboratories. They will be asked specifically not to pre-select good examples of individual diagnostic categories but to adhere strictly to number sequences. A total of 110 slides will thus be provided by each of the 56 laboratories resulting in a total of 6,160 slides in this arm of the study. Laboratories will have 3 months to gather and submit these slides.

Cases reported as inadequate because of the absence of transformation indicators following previous treatment of CIN, or the absence of endocervical cells in the case of previously treated CGIN will be specifically excluded from the study as the reason for inadequacy does not relate to specimen cellularity.

It is recognised that mucus and blood may block the filter pores in the Cytyc ThinPrep® LBC system. This problem should be addressed in routine work by the pre-treatment of the sample prior to a repeat preparation being made. The study will collect both the original preparation and any repeat preparations which have been made.

If additional preparations have been made, then all available slides should be submitted and included within the category of the issued cytological report, irrespective of the appearance of individual slides.

Given the numbers of slides which will be gathered during the various parts of the study, it is critical that they are handled in such a way as to preserve patient anonymity; to be fully compliant with the Data Protection Act 1998; with the Human Tissue Act 2004; and to ensure that all slides can be traced and rapidly returned to the originating laboratory if required for clinical review. To facilitate these requirements, all laboratories will be provided with a Preparatory Package that will include:

- A full written protocol for this part of the study with contact details for the Study Centre to obtain advice if required.
- A laboratory anonymisation code e.g. lab code AA
- A floppy disc or CD pre-loaded with a database listing cases 1-20 in 3 of the diagnostic subgroupings and 1-50 for negative cases. Laboratories will be required to enter the slide laboratory accession numbers against the appropriate entries in the database and to ensure that this process is subject to quality control. The details should be saved as a password-protected file and the floppy disc/CD stored in a locked cabinet. Hence only the originating laboratory will have access to named patient details.
- 110 pre-printed slide labels giving study name, the laboratory anonymisation code, diagnostic category and case number. See Figure 1. (Spare labels will be provided for any additional slides. The laboratory will need to add the slide diagnostic category, numerical sequence, lab code and be asked to suffix the slide number with "a" e.g. slide 15a.) These must be applied to the slides to cover the existing laboratory labels. The database will be used to ensure that the correct label is applied to each slide. This step should be double checked to ensure accuracy.

- 5 Slide transport boxes (each with capacity for 25 slides) pre-labelled with study name, laboratory anonymisation code.
- A paper check list will be produced by the database to accompany slide boxes to confirm that the full complement of 110 slides (plus details of any additional slides) has been sent
- Pre-labelled padded packaging

On receipt at the Study Centre, all slide sets will be checked to ensure they are complete; that there has been no damage in transit; and that the slides have been labelled in accord with instructions. Thereafter slides will be relabelled with an anonymised code and placed in a further set of 275 transport boxes in a pre-determined randomised order, established by the study statistician. Boxes will therefore contain a mixture of different diagnostic groupings from different originating laboratories. The anonymisation code will be abased on the lab to which the slides are being sent, the bax they are eneterd in and the position within the box. Details of the content of each box will be held in a secure database.

A further database will be established which will again be provided to each participating laboratory as an individualised CD. Each disc will contain details of the anonymised slide set allocated to that laboratory and will allow direct entry of the individual cell counts for each slide (number to be determined – see below); whether transformation zone (TZ) material (metaplastic squames or endocervical cells) is detected; and details of the eyepiece magnification, FN value of the microscope

[figure not shown]

Figure 2 - Diagrammatic representations of Cvtvc and SurePath preparations

used for that individual slide assessment, and the start point for the cell count based on clock face e.g 12 o'clock, 3 o'clock. The laboratories will not be required to calculate the total cellularity for each slide. This will be calculated at the Study Centre using the following formula:

Total cell count = mean cell count x area of cell deposit x area of ocular

The boxes will be sent in sets of 5 with the corresponding CDs to each of the participating laboratories via courier. All details including the date and time of despatch will be recorded electronically.

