# Sample Size

Declared inadequate slides will be used to determine the distribution of cellularity in such slides. With a sample of 1,120 a proportion of say 5% falling above the specified threshold can be estimated with a 95% distance from the percentage to the 95% c.i. of 1.3%. Declared negative slides will be used to estimate the proportion falling below the specified threshold. With 2,800 slides a proportion of 1% falling below the required threshold can be estimated with distance from the percentage to the 95% c.i. of 0.4%. We hypothesise that the greatest proportion of slides with low cellularity will be seen in mildly dyskaryotic slides and lowest proportion in negative slides, with high-grade dyskaryotic slides between the two. With 2,800 negative slides, 1,120 high grade and 1,100 mildly dyskaryotic slides, a chi-squared test of trend will have a power of 87% to detect a difference between 1% of negative slides falling below a threshold increasing to 2.5% in the mildly dyskaryotic cases and a power of 74% to detect an trend increasing from 1% to 2%.

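### Part 1 excludes inadequates for only two non-cellularity reasons and records no reason for the rest, so the proportion of inadequates above a laboratory's cell threshold may overstate non-adherence

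*Protocol*

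**What the plan says.** In the Protocol's Laboratory Practice Survey, recruitment is described as "giving a total of 56 laboratories (28 laboratories for each system". Under Slide Survey, each laboratory "will be asked to submit 20 consecutive cervical screening LBC cases from each of the following report categories: inadequate, mildly dyskaryotic and high grade", in strict number sequence. Two kinds of inadequate case are left out. The first is described as "Cases reported as inadequate because of the absence of transformation indicators following previous treatment of CIN"; the second is missing endocervical cells after treated CGIN. The ground given is that these cases "will be specifically excluded from the study as the reason for inadequacy does not relate to specimen cellularity".

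The same section lists what accompanies or describes each case: an accession database kept at the laboratory, slide labels, a paper checklist sent with the boxes, and a disc for entering counts, transformation-zone material and microscope details. None of these lists the reason why a case was reported inadequate.

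On use, the part 1 Sample Size section says: "Declared inadequate slides will be used to determine the distribution of cellularity in such slides". For precision it then takes 1,120 slides and an illustrative 5% above the threshold, and puts the half-width of the 95% confidence interval at 1.3 percentage points. The part 1 Statistical Analysis section models the proportion either side of the threshold, using each laboratory's current threshold and the one derived in part 2. Outcome Measures reads the result as how well laboratories meet their declared criteria and the levels from part 2.

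**The concern.** The stated ground for exclusion is a general principle: a case whose inadequacy has nothing to do with cell numbers does not belong in this part of the study. It is applied to two post-treatment situations only, and every other inadequate enters by consecutive sampling.

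The Protocol itself leaves room for other grounds. Background and Introduction calls squamous cell content the primary indicator of adequacy, not the sole one. The questionnaire in Laboratory Practice Survey asks for adequacy criteria, of which the declared threshold is one. A slide with enough cells can therefore be reported inadequate in full accordance with a laboratory's own procedure. When that slide is compared with the laboratory's cell threshold, it falls on the wrong side and looks like a departure from declared practice.

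At stake is the part 1 comparison of declared and actual practice, including any reading of which laboratory procedures work better. Procedures and questionnaire answers are held per laboratory, so as covariates they cannot reclassify an individual slide.

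**Working it through.** **Inputs from the Protocol.** 56 laboratories and 20 inadequates each (Laboratory Practice Survey; Slide Survey); an illustrative proportion above threshold p = 5%, n = 1,120 and a stated half-width of 1.3 points (part 1 Sample Size).

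**Inputs not in the Protocol (assumed).** f = share of submitted inadequates reported for another non-cellularity reason, taken as 5% and 10%. a = share of those slides with a count above the threshold, taken from 0.5 to 1.0. The 5% is used here as the proportion above threshold among the cellularity-related inadequates.

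**Step 1: reproduce the stated figure.** 56 × 20 = 1,120. Half-width = 1.96 × √(0.05 × 0.95 / 1,120) = 0.01276, or 1.28 points. This agrees with the stated 1.3, so the sample-size arithmetic is right. The problem lies in which slides enter the proportion.

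**Step 2: proportion observed when such slides stay in.** Observed = (1 − f) × 0.05 + f × a.

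| f (assumed) | a = 0.5 | a = 1.0 |
|---|---|---|
| 5% | 0.0475 + 0.025 = 7.25%, or 7.3% | 0.0475 + 0.050 = 9.75%, or 9.8% |
| 10% | 0.045 + 0.050 = 9.5% | 0.045 + 0.100 = 14.5% |

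**Step 3: direction.** Bias = f × (a − 0.05). It is positive whenever these slides exceed the threshold more often than the 5% baseline.

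**Step 4: how few slides matter.** Setting the bias equal to the half-width gives f = 0.01276 / (a − 0.05).

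- a = 0.5: f = 0.01276 / 0.45 = 2.8%, about 32 slides.
- a = 1.0: f = 0.01276 / 0.95 = 1.3%, about 15 slides.

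Even 32 slides over 56 laboratories is 0.57 per laboratory, fewer than one each.

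**Step 5: precision if the estimate is restricted.** If 5% of the 1,120 are set aside and not replaced, 1,064 remain, and the half-width is 1.96 × √(0.0475 / 1,064) = 1.31 points. If 10% are set aside, 1,008 remain and it is 1.35 points.

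**The case against.** **The blood and mucus sentence does not support an upward bias.** The Slide Survey says: "It is recognised that mucus and blood may block the filter pores". A reader might infer that bloody or mucoid ThinPrep slides are cellular but obscured, so that the bias falls on ThinPrep and distorts the comparison of systems. The text does not support this. It concerns filter blockage, which would tend to lower the count and put the slide below the threshold. The same paragraph expects pre-treatment and a repeat preparation, and the study keeps both. The direction of any between-system difference is therefore uncertain. This objection stands.

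**The size is assumed.** The Protocol does not say how often laboratories report a sufficiently cellular slide as inadequate. The 5% is an illustration for all declared inadequates, not an expected rate in a cleaned subset. Counting procedures are still to be agreed under Cell Counting, and if only well-seen cells were counted, obscured slides could count low. This stands too, and it is why a range is given. Quoting only the upper ends would assume that every such slide lies above the threshold.

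**Consecutive inadequates are a fair population for describing cellularity.** For the stated objective of describing cellularity in samples deemed inadequate, this is correct, and nothing needs to be removed there. It does not answer the comparison with each laboratory's threshold, where the reason for inadequacy decides whether a high count is a departure.

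**The consequence is limited and can be recovered.** A reader might infer that the recommended adequacy threshold is contaminated. It is not: that comes from the part 2 pick-up model. Nor are the slides lost to later classification, because the laboratory keeps the link from case number to accession number. Recovery would, however, mean going back to each laboratory.

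**Conclusion.** The concern holds for the part 1 estimate of inadequates above each laboratory's current threshold. The exclusion covers only missing transformation indicators after treated CIN and missing endocervical cells after treated CGIN; it should not be read as covering absent transformation-zone material in general. Other non-cellularity inadequates remain, and the data listed for collection do not identify them. Any that exceed the threshold would be read as non-adherence.

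The bias is upward provided that these slides exceed the threshold more often than the cellularity-related inadequates do. Its size rests on assumed shares, and the ranges under the working are illustrations, not predictions. The firmer statement is how little is needed: 1.3% to 2.8% of the inadequates would match the whole stated sampling half-width. The documents do not support a claim about which LBC system is affected more. The descriptive distribution of cellularity and the part 2 threshold do not depend on this point.

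**What to change.** Before slides are gathered, ask each laboratory to enter the reported reason for inadequacy, by study case number, on the checklist that travels with the slide boxes. Adding it only to the accession database would not be enough, because that file stays password-protected and locked at the laboratory. Estimate the proportion above each laboratory's threshold in slides reported inadequate for low cellularity, and tabulate the other reasons separately. Keep all submitted inadequates for the descriptive distribution of cellularity.

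The cost is one extra item for 20 cases per laboratory, that is 1,120 entries in all, and a slightly smaller denominator for the adherence estimate. If 5% or 10% of slides were set aside, the half-width would rise from 1.28 to about 1.31 or 1.35 points. Cell counting and slide circulation do not change.

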# **Statistical Analysis**

Statistical analysis would be used estimate the proportion of slides falling above or below the specified threshold. Covariates for smear result, "LBC system" and relevant data from the survey of practice would be included as covariates in logistic random effects model of the proportion falling either side of the specified threshold. This analysis would be carried out using each laboratory's current threshold and that derived in part 2 of the study.

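### Part 1 files every preparation under the issued report, so superseded low-cellularity first slides, mainly ThinPrep, can count as declared negatives below threshold

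*Protocol*

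**What the plan says.** The Slide Survey section requests one set of cases per laboratory. For negatives: "50 consecutive negative cervical cytology LBC cases from the same time period will also be requested from each of these laboratories". It gives 110 slides per laboratory and 6,160 in all, which is one slide per case.

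On repeat preparations the same section says: "It is recognised that mucus and blood may block the filter pores in the Cytyc ThinPrep". It expects pre-treatment and a repeat, and adds: "The study will collect both the original preparation and any repeat preparations which have been made". The filing rule for additional preparations of any kind is that "all available slides should be submitted and included within the category of the issued cytological report, irrespective of the appearance of individual slides". Additional slides get a label with the suffix a.

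The Part 1 Sample Size section sets the quantity for the negative group: "Declared negative slides will be used to estimate the proportion falling below the specified threshold". It plans for 2,800 slides. The Part 1 Statistical Analysis section is also per slide. It sets out to "estimate the proportion of slides falling above or below the specified threshold", with smear result and LBC system as covariates in a logistic random effects model. The Part 1 Outcome Measures section reads the result as how well laboratories meet their declared criteria.

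**The concern.** The report category belongs to the case, but the quantity analysed belongs to the slide. Suppose a first preparation has few cells, the sample is re-prepared, and the case is reported negative on the repeat. Under the filing rule both slides are declared negatives. If the first slide is below the laboratory's threshold, it is scored as a departure from the declared criterion, although the laboratory may not have relied on it.

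Three uses of the data are exposed:

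- **Adherence.** The proportion of negatives below threshold would partly measure how often laboratories re-prepare.
- **LBC system.** The named cause of repeats is specific to ThinPrep, so the system covariate could pick up a preparation effect that reads as a reporting difference.
- **Other comparisons.** The rule also covers the mild and high grade groups. It therefore reaches the trend test, the comparison with the ARTISTIC/MCM counts, and the use of these cohorts to describe screening sensitivity by cellularity. A superseded low-count slide from an abnormal case would appear as an abnormality reported at low cellularity.

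Cases with repeats would also contribute several correlated slides.

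**Working it through.** **Inputs from the protocol.** There are 56 laboratories, 28 per system, with 50 negative cases each. That gives 56 x 50 = 2,800 negative cases, of which 28 x 50 = 1,400 are ThinPrep. The assumed proportion below threshold is 1%, so 28 slides overall and 14 in ThinPrep.

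**The plan's own precision.** The protocol states that "a proportion of 1% falling below the required threshold can be estimated with distance from the percentage to the 95% c.i. of 0.4" percentage points. Check: 1.96 x sqrt(0.01 x 0.99 / 2,800) = 0.369 points, which agrees after rounding.

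**Inputs not in the protocol (assumptions).** r is the share of ThinPrep negative cases with a superseded first preparation. q is the share of those first slides below threshold. Assume one extra slide per such case, no repeats in SurePath, and a true rate of 1% in both systems.

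**Formulas.** Extra slides = 1,400r, of which 1,400rq are below threshold.

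- Overall proportion = (28 + 1,400rq) / (2,800 + 1,400r)
- ThinPrep proportion = (14 + 1,400rq) / (1,400 + 1,400r)
- Overall bias = 1,400r(q - 0.01) / (2,800 + 1,400r), which is positive whenever q exceeds 1%

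| r | q | Extra slides | Below threshold | ThinPrep | Overall | Overall bias (points) | Bias / 0.369 |
|---|---|---|---|---|---|---|---|
| 0.5% | 25% | 7 | 1.75 | 1.12% | 1.06% | 0.06 | 0.16 |
| 1% | 50% | 14 | 7 | 1.49% | 1.24% | 0.24 | 0.66 |
| 1% | 100% | 14 | 14 | 1.98% | 1.49% | 0.49 | 1.34 |
| 2% | 50% | 28 | 14 | 1.96% | 1.49% | 0.49 | 1.32 |
| 2% | 100% | 28 | 28 | 2.94% | 1.98% | 0.98 | 2.66 |

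**Break-even.** Setting the overall bias to 0.004 gives r = 2,800 x 0.004 / [1,400 x (q - 0.01 - 0.004)]. With q = 50% this is 11.2 / 680.4 = 1.6%. With q = 100% it is 11.2 / 1,380.4 = 0.8%.

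**System comparison.** SurePath stays at 1.0%. A simple two-sided 5% comparison of two proportions, ignoring clustering by laboratory, would declare a system difference with probability of about 5%, 21%, 57%, 56% and 96% in the five rows. It is a rough guide only, since the planned model has random effects.

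**Trend test.** Apply r = 2%, q = 50% to the ThinPrep half of all three groups, with equally spaced scores and high grade midway between negative and mild. Approximate two-sided power for 1% rising to 2.5% falls from 92% to 85%. The 92% comes from this approximation; the protocol states 87%. Only the size of the fall matters here.

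**With the reported preparation only.** The rate returns to 28 / 2,800 = 1.0% overall and in each system, with a half-width of 0.37 points.

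**The case against.** The strongest reply is that the filing rule governs collection, not analysis. The planned numbers are one slide per case, the checklist for each laboratory lists additional slides apart from the 110, and a statistical analysis plan that is not shown could say how repeats are handled. This does not dispose of the point. The rule assigns each slide the category by which it is later analysed, the stated estimates are per slide, and no section takes the extra slides out. Anyone following the protocol as written would include them.

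Several other objections do stand:

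- A reader might infer that laboratories rejected these first slides. The protocol does not say so. It does not say that a blocked filter leaves a slide below threshold, and a report may rest on more than one preparation.
- A reader might infer that the planned precision is certainly exceeded. That depends on r and q. At r = 1%, q = 50% the bias is inside the half-width.
- The 1% to 2% effect in the Sample Size section is a trend from negative to mildly dyskaryotic slides, so it is not a benchmark for a system difference.
- The filing rule is not limited to ThinPrep; only the named cause of repeats is.
- The rule fits the instruction not to pre-select good examples. Letting laboratories choose the reported slide by judgement would weaken that protection.

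**Conclusion.** The point holds as a defect in a stated rule. Filing by case and analysing by slide lets superseded first preparations enter the report categories. In the negative group this raises the proportion below threshold whenever q exceeds the assumed 1%, and mainly in ThinPrep if filter blockage is the chief cause of repeats.

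The direction is clear under that condition, but the size is not established. The overall bias ranges from negligible (0.06 points) to more than twice the planned half-width (0.98 points) over the assumptions shown. It reaches 0.4 points at r of about 0.8% to 1.6%, for q from 100% down to 50%. The baseline is low enough (28 slides) for a few dozen extra slides to matter. The effect on the trend test is modest when all groups are affected alike.

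It is tempting to call this a known bias in the main Part 1 result. The protocol supports neither part of that: it does not rank its Part 1 estimates, and it gives neither r nor q.

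**What to change.** Continue to collect every preparation. Add to the submission database, for each slide, the preparation order and whether the issued report rested on it. Laboratories should complete this from their records at submission, not by looking at the slide again.

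State in the Part 1 analysis that:

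- the report-category analyses take the case as the unit and use only the preparation(s) on which the report rested, with a stated way of combining them when there is more than one;
- where the record does not show this, a fixed rule applies, for example the last preparation made;
- a sensitivity analysis includes all slides with a case-level random effect (this handles the correlation but would not by itself remove the misclassification);
- the remaining preparations are reported separately by LBC system.

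The suffix a should not decide exclusion. It marks only an additional slide, which could be the very repeat that was reported.

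The cost is one extra field for laboratories, a few lines of analysis text, and some cases with incomplete records. It is best done before submission. Afterwards slides are relabelled and recoded, and only the originating laboratory holds the link to its accession numbers.
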